3.1.2 Breath Sensor App

The Breath Sensor App (BSA) for smartphones is required for the breath sensor to communicate with the subject's smartphone and allows basic viewing of CO sample values. The CO breath sample values are presented in parts per million (ppm) within color coded bars (see Figure 2). A low level in a smoker (CO value of 0-6 ppm, Green) does not mean it is safe to smoke. Likewise, a non-smoker may have CO levels higher than 6 ppm (Orange or Red) due to environmental exposure. These ranges are derived from many clinical studies using point measurements at various times of the day ______. Should the subject submit a breath sample using improper technique, s/he will receive an error message in the CO Log.

The results in the app are stored in a secured database. Study personnel will be able to view these results as well as activity in the app.

The app has features to allow the subject to set reminders, vibration, volume, and other preferences.

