4.2 Study Endpoint

Primary endpoint:

- Phase completion of those who started a phase, the proportion who completed that phase, assessed for each phase of the Pivot program.
 - Phase completion is defined as completing the last in-app activity from that phase
 - Exception: completion of Secure is defined as being in Secure for 11 weeks, and having engaged with the program at least once within Secure (app open, daily check-in, responds to coach, logs cig), and providing smoking status (cigarettes per day and 7-day point prevalence) in the end-of-Secure questionnaire

Additional endpoints include:

Engagement:

- Weeks of active engagement
- Number of app opens
- Phase completion proportion of intention to treat (ITT) cohort that completes each phase
 - ITT cohort comprises participants who signed informed consent and completed onboarding in the Pivot app (i.e. downloaded the BSA and Pivot apps, completed device set-up, and completed the three guided breath tests, or GBTs)
- Program completion proportion of intention to treat (ITT) cohort who have been in Secure for 11 weeks and have engaged with the program at least once (open app, or complete a daily check-in, or respond to coach, or log a cigarette), and, provides smoking status (cigarettes per day and 7-day point prevalence) in end-of-Secure Survey

Smoking Behavior:

- Number of cigarettes smoked per day
- Quit attempts (participant did not smoke for at least 24 hours)
- Quit rates: 7-day, 30-day point prevalence

CONFIDENTIAL

- Assessed in the ITT cohort
- Assessed in the Per Protocol cohort (individuals who complete the end-of-phase survey in the phase during which the question is being asked or, complete the exit survey at the end of their engagement with the app, whichever occurs first)
- Sustained quit (continuous days quit)
 - Assessed in the ITT cohort
 - Assessed in the Per Protocol cohort
- Smoking reduction (in participants who do not quit smoking) proportion who achieved 50% cigarettes per day (CPD) reduction or more at study exit

Responses to questionnaires:

- Measurements assessing attitude toward smoking
 - o Readiness to quit
 - Goals related to smoking behavior
 - Confidence to quit
 - o Difficulty maintaining quit
- Net Promoter Score (NPS)
- NPS, for coaching
- Nicotine Dependence
- · Quality of Life

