4.3.1 Criteria for All Participants

All participants must meet all inclusion criteria:

- 18-65 years of age
- English speaking
- Smokes daily
- Smokes 5 or more cigarettes per day
- Owns and uses a smartphone (iPhone 5 and above, operating system iOS 9.0 and above, or, Android 4.4 and above, operating system Android 4.4 and above)
- Employed at least 20 hours per week
- Lives in the USA
- Understands and willing to sign the Informed Consent Form

While pregnant women are not specifically sought in this study, pregnancy is not an exclusion criterion, and pregnant women would be eligible should they meet the inclusion criteria and wish to participate. Pregnant women would be considered eligible for the following reasons: the risk profile of the device, the fact that recording smoking in the study is by self-report and the CONFIDENTIAL

modest participant stipend is not linked to smoking in any way, and potential participants reach out to the study team if they are interested in participating (i.e. recruitment is passive and wholly at the initiation of potential participants, who the study team have no visibility to unless contacted by the potential participant). While participants are deemed eligible to enter the study based on their self-report of smoking at least 5 cigarettes a day, they are not required or asked to smoke any particular amount (or at all) over the course study. Participants are asked to provide breath samples in the CO Breath Sensor device throughout the day, as they are able.

The general study (n=260) will employ non-proportional quota sampling as follows to ensure the study population mirrors the expected initial intended user population:

Age	18-29 year olds	30-60 year olds	61-65 year olds
	< 20 % of sample	Remainder	< 10 % of sample
Cigarettes Per Day (CPD)	5-10 CPD	11-30 CPD	> 30 CPD
	< 25 % of sample	Remainder	< 10 % of sample
Stages of Change*	Quit 30 days	Quit 6 months	Not interested
	≥ 20% of sample	≥ 20% of sample	≤ 20 % of sample
Sex	Male 40-60%	Female 40-60%	

^{*}Stages of Change question and answer choices: Are you seriously thinking of quitting smoking? A. Yes, within the next 30 days B. Yes, within the next 6 months C. No, not thinking of quitting

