Cigarette logging	Daily check-in asks if user smoked previous day, if so, then directs them to log cig.
Suggested breath CO sampling protocol	No explicit sensor use schedule, but sensor is incorporated as follows: • Encourage people who find the 3 times a day useful to keep doing that. • Allow users to set their own milestones, some can be sensor related. Pivot app also gives trophies for breath samples associated with abstinence to augment this. "Take a breath samples to celebrate your smoke-free success."
Coaching frequency	 3-4 coach-initiated interactions per week for the first 3 weeks For users who achieve 30day PP at 3 weeks or 7 weeks in Secure, coaching frequency drops to once weekly, until/unless user indicates lapse or relapse.
Study management	 For the first 3 weeks: If participant does not use the app at least once in 7 days (no cig logging, or CO sampling, or start/complete activity, or start/complete challenge, or complete daily check-in, or respond to coach outreach), study staff will email on day 9, text on day 10, call on day 12, and call on day 14 For the remaining 7 weeks: If participant does not use the app at least once in 14 days (no cig logging, or CO sampling, or start/complete activity, or start/complete challenge, or complete daily check-in, or respond to coach outreach), study staff will email on day 16, text on day 17, call on day 19, and call on day 21

The following table details the different questions being asked of participants at specific time points over the course of the study.

		1	1	1	T	I	I	1	1	T
	Baseline	Explore	Build	Mobilize	Quit (1wk)	Secure - 1wk (2wk post Quit)	Secure - 3wk (1mo post Quit)	Secure - 7wk (2mo post Quit)	Secure - End (3mo post Quit)	Follow -up (6mo)
Cigarettes per day	х	Х	Х	х	х	Х	Х	Х	х	х
Tobacco Forms Used	Х		Х		Х		х	Х	Х	Х
Readiness to Quit (1-10)	х	Х	Х	Х						
Success, if were to quit (1-10)	х	х	Х	Х						
Difficulty staying quit, (1-10)	Х	Х	Х	Х						
Quitting Goal	х	Х	Х	х						
Nicotine Dependence		Х		Х						
7day Point Prevalence					х	х	х	Х	Х	х
30day Point Prevalence							х	Х	Х	х
Date of Last Cig					Х	Х	Х	Х	х	Х
Longest Smoke- free Interval					Х	X	X	Х	Х	Х
Quit Attempts					Х	Х	Х	Х	х	Х
NPS		Х	Х	Х	Х				х	
Coach NPS		X	Х	Х	Х				Х	
Quality of Life	Х								Х	Х
Cessation Medications	х			Х	х	×	×	Х		Х

Participants will receive an email, text or phone call from study staff to inform them they have a questionnaire to complete (

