5.4 Exit

Three months after completing Secure or 3 months after the last engagement with the Pivot app (whichever comes first), the participant is asked to complete the final follow-up questionnaire and return the CO Breath Sensor in the provided pre-paid package. Upon completion of the final survey and return of the CO Breath Sensor, the study will be considered complete.

6 Study Results

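### The 7-day and 30-day quit rates, which are additional endpoints, rest on self-report alone, and no planned analysis compares a claimed quit with the CO sensor that every ITT participant has used.

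*Combined protocol and SAP*

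**What the plan says.** Section 4.2 makes phase completion the primary endpoint. Among the additional endpoints it lists "Quit rates: 7-day, 30-day point prevalence", assessed in the ITT and Per Protocol cohorts, with no CO criterion attached.

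The source of these rates is the participant's own answer. The question table in section 5.3, introduced by "The following table details the different questions being asked of participants at specific time points over the course of the study", asks for 7-day point prevalence from the Quit phase to the 6-month follow-up and for 30-day point prevalence from week 3 of Secure onward. Section 4.3.1, in explaining why pregnant women are eligible, refers to "the fact that recording smoking in the study is by self-report".

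On the sensor, the documents say the following.

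- Sections 4.2 and 5.2: entry to the ITT cohort requires three guided breath tests.
- Section 3.1.2: readings go into a secured database that study personnel can view. The green band is described in the words "A low level in a smoker (CO value of 0-6 ppm, Green", with a warning that non-smokers can exceed 6 ppm through environmental exposure.
- Section 5.3, Secure: "No explicit sensor use schedule, but sensor is incorporated as follows".
- Section 5.4: at the end "the participant is asked to complete the final follow-up questionnaire and return the CO Breath Sensor".

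Section 6.2 names a one-sample t-test for numerical data and Fisher's exact or chi-square tests for categorical data. It gives no CO comparison, no cut-off and no rule for a reading that disagrees with a reported quit.

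**The concern.** A quit rate based only on what participants say is biased upward if some report abstinence while still smoking. Several features make that direction more plausible than its opposite. The study is open-label, the coach supports the quit and celebrates smoke-free milestones, and participants serve as their own controls, so no comparator arm shares the reporting bias.

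Section 4.10 justifies the sample size partly by confidence intervals adequate for historical comparisons. A confidence interval covers sampling error and not misreporting. If quit rates are among the figures compared, a reader needs to know how abstinence was verified before setting them beside another study's rate.

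The means of a partial check are already in the participant's hands. In Secure the app even awards trophies for breath samples that fit with abstinence, so CO is used to reward a quit but not to examine the quit endpoint.

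**Working it through.** **1. The plan's own figures.** The documents give no expected quit rate, no false-report rate, and no alpha, power or standard deviation, so there is no quit-rate calculation to reproduce. The only related figures are in section 4.10: 260 enrolled and 100 or more completing the last time point. 100/260 = 38.5%.

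**2. Which CO readings would exist when abstinence is asked about.**

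| Time point | Abstinence question | CO sampling in the plan |
|---|---|---|
| End of Quit | 7-day | Three breaths a day suggested, plus one at each craving |
| Secure, weeks 1, 3 and 7 and end | 7-day; 30-day from week 3 | No explicit schedule |
| Exit (6 months) | 7-day and 30-day | Not marked in the Schedule of Study Activities |

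Stored readings may cover the end-of-Quit question well. At end-of-Secure and exit they may be sparse or absent, so a check there needs an invited sample. It is feasible because the sensor is still held until participants "complete the final follow-up questionnaire and return the CO Breath Sensor in the provided pre-paid package".

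**3. Size, from assumed inputs.** Let R be reported quits, N the ITT size and f the share of claims that CO contradicts. The rate after removing contradicted claims is R(1 − f)/N. N = 260 is from section 4.10. R and f are assumptions, and using all 260 as the denominator assumes that people with no answer count as not quit.

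With R = 40, the reported rate is 40/260 = 15.4%:

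- f = 0.10: 36/260 = 13.8%
- f = 0.20: 32/260 = 12.3%
- f = 0.30: 28/260 = 10.8%

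The 95% Wilson interval for 40/260 is about 11.5% to 20.3%. The first two results lie inside it and the third lies below it.

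With R = 78, the reported rate is 30.0% (Wilson 24.8% to 35.8%):

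- f = 0.05: 74/260 = 28.5%
- f = 0.10: 70/260 = 26.9%
- f = 0.20: 62/260 = 23.8%
- f = 0.30: 55/260 = 21.2%

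Here f = 0.20 already falls below the interval. The gap of 16/260 = 6.2 points exceeds the normal-approximation half-width of 5.6 points. At n = 100 the same case gives 24/100 = 24.0% against an interval of 21.9% to 39.6%, so sampling error dominates.

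Over assumed reported rates of 20% to 40% and f of 5% to 30%, the overstatement at N = 260 runs from 1.2 to 11.9 points.

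**4. Why the check should not use every reading in the week.** Three breaths a day for seven days is 21 readings, before any taken for cravings. A rule that no reading may exceed 6 ppm gives such a person at least 21 chances of one environmental exceedance, against one chance for someone who samples once. True quitters who sample most would be contradicted most often. At the end-of-Quit questionnaire the 7-day look-back also reaches the quit date, so readings that reflect smoking before the quit could count against a true quitter.

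**The case against.** The other side has a good case on several points.

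- **Endpoint rank.** Quit rates are additional endpoints. Completion of Secure does require "providing smoking status (cigarettes per day and 7-day point prevalence) in the end-of-Secure questionnaire", but it requires an answer and not a true one, so the primary endpoint is untouched. A reader might infer that the main result is compromised; it is not.
- **Payment.** A reader might infer that paid questionnaires encourage false quits. The documents do not support this: section 4.3.1 says the stipend is unconnected with smoking, and section 4.5 ties payment to completing questionnaires and returning the sensor, whatever the answers. Payment is no part of the argument.
- **Stored data.** A reader might infer that the existing database would settle the matter. It would not, because sampling is voluntary in Secure and unscheduled at exit. For people who left the app, exit comes 3 months after their last engagement.
- **Undetected.** Staff can view readings and might notice a discordant one. What is missing is any requirement to look, count or report.
- **Historical comparators.** Section 4.10 does not name them. If they are self-reported quit rates, self-report is the like-for-like measure. This is a reason to keep it as the main rate, and it does not argue against a check beside it.
- **What CO can show.** By section 3.1.2 a smoker can read 0-6 ppm and a non-smoker can read higher. CO reflects recent smoking only, so it cannot verify a 30-day or sustained quit. Sampling is remote and unsupervised, and nothing confirms who gave the breath.

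These points limit the weight of the concern and shape the remedy. None supplies the missing comparison. Self-report is openly declared, so nothing is concealed; the gap is that an available check goes unused.

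**Conclusion.** The point holds as a moderate one. The 7-day and 30-day quit rates depend on self-report alone, and neither section 4.2 nor section 6.2 compares a claimed quit with CO, although the sensor is in use and kept to the end. Over-reporting would bias these additional endpoints upward unseen, in a design with no comparator arm to absorb it.

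The amount is unknown. The range of 13.8% to 10.8% from a reported 15.4% rests on an assumed 40 quits and an assumed 10% to 30% contradicted. A reader might take it as an estimate of the bias; the documents give nothing to estimate it from. That over-reporting is the likelier direction is an inference from the coaching and the design and not a finding. The primary endpoint is unaffected.

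**What to change.** Keep self-report as the main quit rate and add a pre-specified sensitivity analysis of 7-day abstinence at two time points, end-of-Secure and exit.

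1. Invite one breath sample with each of those questionnaires, at exit before the sensor is returned.
2. Classify each claimed quit by that sample or, if none is given, by the stored reading nearest the questionnaire within the 7-day window: CO-supported, CO-contradicted or no-sample.
3. Fix the cut-off in advance. The app's 0-6 ppm band is the only one in the documents, and it is a display band, so the choice should be justified.
4. Allow a repeat sample after a high reading. Do not classify on the maximum of the week's readings. Never count no-sample as supported.
5. Report all three counts and the CO-supported rate beside the self-report rate. The counts matter because the CO-supported rate alone mixes contradiction with failure to sample.
6. State the limits: recent smoking only, no verification of 30-day or sustained quits, overlap of smokers and non-smokers around 6 ppm, unsupervised sampling, and participants who do not sample.

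The cost is protocol and analysis wording, two invited breaths and any repeats, on a device already in hand, with no visit. The exit sample has to be arranged before sensors are returned, because the chance is then lost.

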Outcomes from a Mobile Smoking Cessation Program During a Monitoring Period of 6 Months

Issue Date: September 29, 2017

Prepared By:	
Sr. Director, Clinical and Medical Affairs, Carrot Inc.	
Approved By:	
	_
President and CEO, Carrot Inc.	
	_
Regulatory Affairs, Carrot Inc.	
VP, Behavioral Science, Carrot Inc.	
Director, Clinical Affairs, Carrot Inc.	

Protocol Summary

Device Names	Carbon Monoxide Breath Sensor System (COBSS) and Pivot App		
Protocol Title	Outcomes from a Mobile Smoking Cessation Program During a Monitoring Period of 6 Months		
Principal Investigators			
Protocol Number			
Protocol Version			
Protocol Shorten Name	6-Month Outcomes of a Mobile Smoking Cessation Program		
Study Design	Prospective, open label, single center clinical study enrolling up to 310 subjects (up to 50 run-in subjects, and 260 general subjects) No medical decisions will be made related to test results.		
Objective	We aim to assess a mobile smoking cessation program delivered through the Pivot Application ('App'). We will evaluate user engagement and retention in the program, attitude towards smoking and smoking behavior, quit rates, relapse rates, and quality of life over the study period, as well as user feedback on the program.		
Potential Subjects	Up to 310 subjects who report daily smoking behavior (smokers).		
Inclusion Criteria	 18-65 years of age English speaking Smokes daily Smokes 5 or more cigarettes per day Owns and uses a smartphone (iPhone 5 and above, operating system iOS 9.0 and above, or, Android 4.4 and above, operating system Android 4.4 and above) Employed at least 20 hours per week Lives in the USA Understands and willing to sign the Informed Consent Form 		

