1.3.3 Risk Benefit Assessment

Given the non-invasive nature of the breath sampling and the data collection, there are no anticipated risks to subject safety. This study assesses a mobile smoking cessation program, which may help subjects decrease or quit smoking. No medical decisions are made based on study data.

2 Study Objective

We aim to assess the Pivot mobile smoking cessation program. We will assess participant engagement with and feedback of the program, as well as changes in attitude towards smoking and smoking behavior over the study period.

3 Device Descriptions

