4.10 Sample Size and Justification

Up to 50 participants will comprise the run-in group. The purpose of the run-in group is to provide baseline observations on the functioning of the BSA and Pivot app, and provide the opportunity to address unforeseen bugs or issues that arise prior to proceeding with the general study.

The target enrollment of 260 for the general study is estimated to yield 100 or more subjects completing the study at the last time point (3 months after the end of Secure). Based on power calculations, this will detect a 50% reduction in cigarettes, a mean change of 1 or greater in ratings assessing attitudes towards smoking, and will provide adequate confidence intervals to make historical comparisons.

5 Study Procedure and Schedule

5.1 Screening and Day 0

Study personnel will verify eligibility by reviewing the potential participant's responses to the Online Screening Form ; eligible participants (applies to both the run-in and general study participants) who meet non-proportional quota sampling needs (applies to general study participants) will then be called by study staff. During this call, any additional needed screening information is obtained, eligibility is confirmed, the study is described and the potential participant has the chance to ask questions. If the potential participant would like to proceed, the online registration form is emailed to the potential participant. Potential participants will be provided an access code at this time to allow access to the website.

Verification of identity and informed consent is performed during the screening phone call and during the online registration process. At this time, potential participants create a user login and password. An email is then generated and sent to the email address provided by the potential participant. To confirm identity, the potential participant must access their email and confirm through the provided link. The potential participant then reviews the electronic informed consent form on their own timeline and is provided study staff contact information should they have any questions. If the potential participant would like to proceed, they electronically sign the informed consent form

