Suggested breath CO sampling protocol	 2 days of "intensive" sampling (hourly) to benchmark – beginning and end of Mobilize Remaining days in between are 3 breaths a day: morning, mid-day, evening 			
Coaching frequency	 Intro touch point to Mobilize with two interactions on completion of specific activities that prepare users for quit day. Wrap-up touch point to review quit plan If a user has not completed activities, milestones and/or has not had a coaching interaction within the past 2 days, the coach will reach out to the user to check in. 			
Study management	If participant does not use the app at least once in 7 days (no cig logging, or CO sampling, or start/complete activity, or start/complete challenge, or complete daily check-in, or respond to coach outreach), study staff will email on day 9, text on day 10, call on day 11, and call on day 13			

Quit				
Duration, pace, key components	 7 days from quit date, time based, activities are unlocked daily Daily check-in introduced Red 'guy' on Pivot app dashboard turns green, Crush-a-Craving button added 			
Intent	 Getting through the toughest week Lapse and relapse handling 			
Activity/content	 Daily check-in, must be completed to access rest of app One activity is unlocked per 24h 			
Cigarette logging	Daily check-in asks if user smoked previous day, if so, then directs them to log cig			
Suggested breath CO sampling protocol	 Encourage light use to see progress 3 breaths a day, morning, mid-day, evening Plus every time user has a craving 			
Coaching frequency	 Intro touch point to Quit with two strategic interactions after completion of smoke-free milestones (Quit: 24 hours and 72 hours) Wrap-up touch point to review progress, celebrate smoke-free milestones and identify areas of the quit plan that may need to be adjusted going forward – guide to move to Secure. If a user has not completed activities, milestones and/or has not had a coaching interaction within the past 2 days, the coach will reach out to the user to check in. 			
Study management	If participant does not use the app at least once in 7 days (no cig logging, or CO sampling, or start/complete activity, or start/complete challenge, or complete daily check-in, or respond to coach outreach), study staff will email on day 9, text on day 10, call on day 11, and call on day 13			

	Secure
Duration, pace, key components	11 weeks from quit dateDaily check-in
Intent	Lapse and relapse handling
Activity/content	Daily check-in with journaling

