6.2 Data Analysis

Data from the run-in participants will be analyzed separately from the data from the general study participants. Both cohorts will be analyzed using the ITT and Per Protocol definitions, and endpoints described previously.

Changes in measurements from baseline, to the end of each phase, to exit will be assessed. Participants will serve as their own controls and comparisons will be made to no change. One sample t-test will be used for numerical data. Fisher's Exact or Chi square will be used for categorical data.

All deviations from the study protocol will be identified, recorded and analyzed.

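### Relapse rates are an objective with no endpoint, and continuous days quit is capped at a survey date that, at exit, depends on when the participant stopped using the app

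*Combined protocol and SAP*

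**What the plan says.** The Objective in the Protocol Summary lists "quit rates, relapse rates, and quality of life over the study period". Section 2 is narrower: beyond engagement and feedback it covers "as well as changes in attitude towards smoking and smoking behavior over the study period" and does not name relapse.

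Neither the Summary's endpoint list nor Section 4.2 contains a relapse endpoint, and no section defines relapse. Quitting is measured by "Quit rates: 7-day, 30-day point prevalence", by quit attempts, and by "Sustained quit (continuous days quit"), the last in both the ITT and Per Protocol cohorts. No time origin, lapse rule, time point or rule for people still abstinent is given.

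Section 6.2 sets the frame: "Participants will serve as their own controls and comparisons will be made to no change". For numerical data it names one method: "One sample t-test will be used for numerical data". No time-to-event method appears.

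The question table in Section 5.3 asks for the date of the last cigarette, the longest smoke-free interval and quit attempts at six times after the quit date. In the Quit and Secure phases, "Daily check-in asks if user smoked previous day, if so, then directs them to log cig". Section 5.4 makes the final questionnaire due three months after the earlier of two events: finishing Secure, or last using the app.

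**The concern.** A named objective has nothing behind it in the endpoint list or the analysis. The 7-day and 30-day rates do not fill the gap. They are cross-sectional, so equal rates at two surveys fit either no relapse or relapses offset by new quits.

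The nearest endpoint, continuous days quit, is right-censored for anyone still abstinent: the survey ends the count, not a cigarette. A plain mean treats that count as complete. A test against zero adds almost nothing, because daily smokers start near zero and the value cannot be negative.

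At exit there is a second problem. Leaving the app early brings the final survey forward, so equal abstinence earns fewer days. Engagement is the domain of the primary endpoint, so a smoking outcome that moves with it can be misread. Section 4.10 also intends historical comparisons, and a mean capped by this trial's survey dates is not comparable with one from another schedule.

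**Working it through.** **The plan's own figures.** None is given for relapse or quit duration. The sample-size statement concerns other outcomes ("Based on power calculations, this will detect a 50% reduction in cigarettes", and attitude ratings). It expects 100 or more of 260 at the last time point: 100/260 = 38.5%, so up to 160 (61.5%) may be absent.

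**Step 1: where the cap is common.** The question table places the in-program surveys at 1 week, 2 weeks, 1 month, 2 months and 3 months after quitting, or about days 7, 14, 28, 56 and 84. People abstinent from the quit date share the same nominal cap at each.

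**Step 2: where it is not.** At exit, take 3 months as 91 days and two people who never smoke after their quit date.
- Finishes Secure: 7 (Quit) + 77 (Secure) + 91 = 175 days.
- Last uses the app on day 14: 14 + 91 = 105 days. 105/175 = 0.60, or 40% lower.
- Last uses it on day 35: 35 + 91 = 126 days. 126/175 = 0.72, or 28% lower.

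The Secure table in Section 5.3 counts its 11 weeks from the quit date, whereas the question table puts Secure week 1 at two weeks after quitting. On the former reading a finisher scores 77 + 91 = 168. Then 105/168 = 0.625 (37.5% lower) and 126/168 = 0.75 (25% lower).

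**Step 3: effect on a mean (illustration only).** Assume exponential time from quit date to relapse, no re-quitting, and λ = ln 2 / median. The true mean is 1/λ. The mean observed up to day C is (1 − exp(−λC))/λ, and the share still quit is exp(−λC).

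| Assumed median | True mean | Mean at day 84 (% of true; still quit) | Mean at day 175 (% of true; still quit) |
|---|---|---|---|
| 30 days | 43 | 37 (86%; 14%) | 43 (98%; 2%) |
| 90 days | 130 | 62 (48%; 52%) | 96 (74%; 26%) |
| 180 days | 260 | 72 (28%; 72%) | 127 (49%; 51%) |

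Now let exit fall with equal probability on day 98, 119, 147 or 175 (last app use on day 7, 28, 56 or 84), with relapse unchanged. Averaging the formula over the four dates gives 40.9, 82.7 and 104.2 days, against 42.5, 96.1 and 127.3 if everyone exits on day 175. The mean falls by 4%, 14% and 18% through disengagement alone.

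**Step 4: which streak.** The calculation above fits the longest streak, or time to first relapse. If the endpoint is the current streak, relapsed people score zero and the mean is C × exp(−λC). At a 90-day median that is 84 × 0.524 = 44 days rather than 62 at the end of Secure, and 175 × 0.260 = 45 rather than 96 at exit. The text does not say which is meant.

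**The case against.** The strongest reply is that the plan is merely terse. Several stronger readings are tempting, and the documents do not support them.

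- A reader might infer that the trial cannot say how long quits last. Only the written analysis cannot. Check-ins, cigarette logs and six post-quit surveys hold the information to the end of Secure.
- A reader might infer that the t-test is prescribed for this endpoint. Section 6.2 does not name it, and its tests address change from baseline, where neither the last-cigarette date nor the longest interval is asked. Descriptive reporting is possible. What stands is that no other numerical method is offered.
- A reader might take survey date minus last cigarette as the only derivation. The longest smoke-free interval is asked directly, though it too is capped at the survey for people still abstinent.
- A reader might extend the unequal caps to every survey. Step 1 shows that they arise mainly at exit.
- A reader might say that quit rates can never yield relapse. Aggregate rates cannot, but records are linked within participants, so transitions can be derived. The plan does not say that they will be.

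The day-14 pair is also constructed: it needs someone who leaves the app, stays abstinent and still answers the exit questionnaire, and nothing indicates how often that happens. Finally, this is a non-primary endpoint in a single-arm study, and Section 2 omits relapse. All of that limits the severity. It does not supply the missing endpoint or the missing rule for people still abstinent.

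**Conclusion.** The point holds as stated in the heading. A stated objective has no definition, endpoint or analysis. Continuous days quit is undefined as to origin and streak and has no censoring rule. At exit it can differ by about 40% (37.5% on the other Secure timing) between two people with identical abstinence.

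The effect on the study mean is not known. Under the assumed exponential model it is small if most people relapse quickly (the exit mean is 98% of the true mean at a 30-day median) and large if many stay quit (49% at 180 days). These figures rest on assumed relapse and disengagement patterns and on 91 days for three months. The primary endpoint, phase completion, is unaffected. The change should be made, but the study's main result does not depend on it.

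**What to change.** **Endpoints (Section 4.2).** List relapse. Define lapse and relapse in terms of the daily smoking records, and fix the time origin as the quit date, stating how a moved quit date is handled. State whether continuous days quit is the current or the longest streak. Reconcile the two descriptions of when Secure starts, since they decide whether it ends on day 77 or day 84.

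**Analysis to the end of Secure (Section 6.2).** Replace any mean or t-test of continuous days quit with Kaplan-Meier curves for time to first lapse and time to relapse, using daily check-ins, cigarette logs and the last-cigarette date. Add continuous-abstinence proportions at fixed days after the quit date, for example 30 and 84, with the later day matched to the reconciled end of Secure.

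**Follow-up.** Do not extend ordinary Kaplan-Meier to this point. Check-ins and logging belong to the program phases, so afterwards only the most recent cigarette is dated and relapse is known only within an interval. Report the proportion continuously abstinent since the quit date, from the last-cigarette date, with the spread of days since quitting, or use an interval-censored method.

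**Cohorts.** In ITT proportions, count people who never set a quit date or are lost as not sustained. Add a sensitivity curve that counts loss as relapse.

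**Cost.** Wording in two sections and some programming, with no new data collection. Two limits remain: smoking status is self-reported, and censoring at disengagement may be informative. The sensitivity curve shows how much the latter could matter but does not remove it.
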